**e) Study setting**

Telephone, outpatient offices, emergency department, Hospital

**f) Primary and secondary outcome measures**

Primary Outcome Measures:

Aim 1 : Rates of Hospitalization

Aim 2 : Rates of Intubation and Death

Aim 3 : Side effect profile

Secondary Outcome Measures:

Aim 1 and 2 : Depression, Anxiety, Suicidal thinking, Days of Illness, Severity of Illness

**g) Variables**

Demographic information (age, gender, medical history, co-morbidities, etc.)
Medications
Symptom profile

 
• Number of days of symptoms prior to testing
 

 
• Epidemiologic information from CDC/Health Department surveillance interview
 

 
• Hospital Course
 

Days in Hospital, Intubation, Complications
Outcome: Never hospitalized, Hospitalized, Intubation, Death

**h) Procedures, interventions, schedule**

Week/Day	Patient Intervention	Setting/ Responsible Individual	Standard of Care	Research Purposes Only
1/1	Informed Consent	Phone/ research team	-----	Yes
1/1	Baseline Study Data	Phone/ research team		Yes
1	Blood Sample	Laboratory Services	Inpatient	outpatient
1	Physician Interview/ Medication Prescription	Phone/Study physician	----	Yes
Daily	Symptom/ Side effect Check In	Phone/ research team		Yes
Weekly	Physician Interview/ Medication Prescription	Phone/Study physician	----	Yes
Weekly or Change in Clinical Status*	Blood Sample	Laboratory Services	Inpatient	outpatient

\*Change in Clinical Status includes outpatient to inpatient, transfer to ICU, and intubation

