#### **d) Justification of the number of subjects**

All power calculations were done with the clincalc program and assume a dichotomous endpoint in a two independent sample study and are based on achieving the standards of a power of 0.80 and with an alpha of 0.05. Please note, that the assumptions of fluoxetine effect size are based on the absolute most conservative values in the published literature reviewed above.

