#### **Aim 1 : Hospitalization rates**

Assumptions:

1. 2/3 of patients who enter the trial will choose to take fluoxetine
2. 10% of COVID-19 + patients will progress to a clinical condition requiring hospitalization
3. Fluoxetine treatment decreases hospitalization rate by 50%

Sample Size : 312 in the no medication group and 624 in the 2 fluoxetine groups, for a total sample size of 936. This sample size is very achievable given the current coronavirus pandemic.

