**Procedures:**

Instrument	Duration	Assessment Time Points	Frequency
Baseline Intake Form Chart Review Form 04/1/19-present Baseline Demographics and past medical history	30 min	Initial study entry	Once
PHQ-9	5 min	Initial Study Entry	Weekly
GAD-7	5 min	Initial Study Entry	Weekly
Columbia Screener-recent	3 min	Initial study Entry	-----
Symptom Checklist	5 min	(included in baseline)	Daily assessments
Columbia Screener – since last visit	3 min	-----	Daily assessments
Physician Interview/Medication Prescription	40 min	Baseline	weekly

Drug Distribution		Once, at entry	monthly
Blood Draw for future assessment of cytokine levels	60 min	Baseline	Weekly, as possible
Chart Review Followup		At study exit, one month, 3 months, 6 months and one year after study exit	See notes to left 5 data points From 4/1/19- 4/1/23

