#### **4) Planned data analysis**

Aim 1, 2, 3 : Descriptive statistics,

Compare rates of primary and secondary outcome measures in subjects receiving fluoxetine with those not receiving fluoxetine by Student t-test and Chi-square test as appropriate.

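### Side effects and suicidal thinking are compared as simple rates with no common observation period, so unequal time under observation can look like a drug effect

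*Combined protocol and SAP*

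**What the plan says.** Section 3 f) makes side effects a primary outcome ("Aim 3 : Side effect profile") and lists suicidal thinking among the secondary outcomes for Aims 1 and 2. Section 3 h) collects side effects through a daily phone "Symptom/ Side effect Check In", and its Procedures table schedules the "Columbia Screener – since last visit" daily as well.

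No length for the daily monitoring appears in the available text. Chart reviews are timed from study exit, but exit is not defined. The 8-week span in the blood draw item limits blood volume only.

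Under section 3 b), participants choose whether to take fluoxetine and may revise that choice every week. Section 4 then plans to "Compare rates of primary and secondary outcome measures in subjects receiving fluoxetine with those not receiving fluoxetine", using Student t-test or chi-square as appropriate. It gives no person-time denominator, censoring rule, missed-call rule or per-person definition of an event.

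Section 3 d), after the Aim 2 sample size, says that Aim 3 and 4 data will serve qualitatively as pilot information. Section 4 includes Aim 3 among the aims to be tested.

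**The concern.** The proportion of people who ever report a side effect grows with the time they are watched. A chi-square comparison of such proportions keeps its 5% error rate under no drug effect only if both groups have the same opportunity to report. Nothing in the available text secures that.

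The design leaves room for imbalance:

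- Groups are self-selected and can change weekly, so one person's days may fall on and off the drug.
- Monthly drug distribution is a contact that only takers need.
- The Study Timeline closes fluoxetine enrolment on 2/1/2021 and overall enrolment on 4/1/2021. If monitoring were cut at a calendar date, the latest entrants, who could only be non-takers, would be observed for less time.

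Aim 3 is the trial's safety question. Longer observation of takers would suggest harm that is not there; shorter observation, for example if people end contact when they stop the drug, would hide harm that is.

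**Working it through.** **1. The plan's own figure.** Inputs from section 3 d): "a power of 0.80 and with an alpha of 0.05"; "2/3 of patients who enter the trial will choose to take fluoxetine", so k = 2 takers per non-taker; "10% of COVID-19 + patients will progress to a clinical condition requiring hospitalization", so p0 = 0.10; and a halving on fluoxetine, so p1 = 0.05. Sidedness is not stated; two-sided is used here.

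n0 = [1.96·√(p̄(1−p̄)(1+1/k)) + 0.842·√(p0(1−p0) + p1(1−p1)/k)]² / (p0−p1)², with p̄ = (0.10 + 2×0.05)/3 = 0.0667.

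This gives 311.6, so 312 non-takers, 624 takers and 936 in total, exactly as stated. That size is for hospitalization; no size or power is given for side effects or suicidal thinking. The 624 and 312 are used below only as group sizes.

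**2. Proportion ever reporting.** Assume no drug effect, the same independent risk q per observed day in both groups, and m days observed. Then P(ever) = 1 − (1−q)^m. The documents give neither q nor m; both are assumptions.

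**3. Chance of p < 0.05.** For the two-sided pooled two-proportion test, with difference d, pooled standard error s0 and unpooled standard error s1, the chance is Φ((d − 1.96·s0)/s1) plus the opposite tail.

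Example, takers 28 days, non-takers 21, q = 0.5%:
- Takers: 1 − 0.995^28 = 13.1%. Non-takers: 1 − 0.995^21 = 10.0%. d = 0.0310.
- Pooled proportion = (312×0.0999 + 624×0.1309)/936 = 0.1206; s0 = 0.0226; s1 = 0.0217.
- Φ((0.0310 − 0.0443)/0.0217) = Φ(−0.61) = 0.27; the opposite tail is negligible.

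| Days observed, takers vs non-takers | q = 0.5% | q = 1% | q = 2% |
|---|---|---|---|
| 28 vs 28 | 5% | 5% | 5% |
| 28 vs 25 | 8% | 12% | 18% |
| 28 vs 21 | 27% | 47% | 72% |
| 21 vs 28 (drug looks safer) | 31% | 50% | 73% |

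For 28 vs 21 days the proportions ever reporting are 13.1% vs 10.0%, 24.5% vs 19.0% and 43.2% vs 34.6%.

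**4. Time observed or calls answered?** If each answer covers the whole gap since the last contact, a call every g days covers g days, and over 28 days P(ever) = 1 − [(1−q)^g]^(28/g) = 1 − (1−q)^28. At q = 0.5% this is 13.1% for g = 1, 2, 4 or 7. For such an instrument the number of calls cancels and only the length of observation matters.

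**5. Why dividing by calls answered is the wrong repair for that instrument.** Give both groups the same 28-day window, with takers answering 28 calls and non-takers 21. Takers report about q per call. Non-takers report the same 28 days of events over 21 calls, about 28q/21 per call. The expected ratio is 21/28 = 0.75 with no drug effect. In simulation with calls missed at random, a Poisson comparison with an offset for calls answered gave a ratio of about 0.76 and rejected falsely about 34%, 57% and 85% of the time at q = 0.5%, 1% and 2%. The plain chi-square stayed near 5%.

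**The case against.** A reader might infer that whichever group answers more calls will report more of everything, suicidal thinking included. The documents do not support that. The daily suicidality instrument is the "Columbia Screener – since last visit" form, so a missed call is made good at the next answered one (step 4). A side effect lasting several days would likewise be caught at a nearby call. Scattered missed calls within a shared window therefore cause less bias than the table shows, and essentially none for the screener. Unequal length of observation and early loss of contact remain.

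A reader might also infer that takers are bound to be seen for longer, so that false harm is the expected error. That is not established either. The weekly physician interview is not restricted to takers, and the weekly PHQ-9 and GAD-7 carry no group restriction. Only monthly drug distribution is clearly specific to takers.

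Three further points are fair:

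- The days and daily risks are assumed, with independent reports at constant risk, so the percentages illustrate a mechanism and predict nothing.
- The participation figure announced in section 3 b) is not reproduced and some pages were removed, so a monitoring length may exist there. It would still leave early loss of contact unhandled.
- The statement in section 3 d) that Aim 3 data are for qualitative use would weaken an argument about false positives. But section 4 plans a test for Aim 3, so the two sections conflict. A t-test on mean scores would also be less exposed than a proportion ever reporting.

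**Conclusion.** The concern holds for unequal time under observation. Side effects and suicidal thinking are collected daily in self-chosen, changeable groups with no common observation period in the available text, and section 4 would compare them without regard to time observed. Under the assumptions in the working, a quarter less observation in one group (21 rather than 28 days) raises the false-positive chance from 5% to between 27% and 72%; a three-day shortfall raises it to between 8% and 18%. With takers observed for the shorter time, the error is of similar size and flatters the drug. The documents contain no contact data, so neither the actual size nor the direction can be stated. The point is worth correcting before analysis; it does not affect the 936, which was sized on hospitalization.

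**What to change.** In section 4, replace the simple comparison of rates for these two outcomes as follows:

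- Define study exit and one common observation window from entry, and define the event per person as the first report.
- Compare the cumulative incidence of first report over that window, censoring each person at the last answered contact.
- Assign observed days to current fluoxetine exposure, because participants may switch weekly.
- Do not use an offset for calls answered when analysing suicidal thinking.
- Report days observed and calls answered by group beside each side-effect table.
- Reconcile the qualitative use of Aim 3 data in section 3 d) with the testing of Aim 3 in section 4.

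The cost is small, since the daily contacts should already supply the records and no sample size changes. The team must settle the window and exit definition, and results become time-based incidences rather than simple percentages. Two limits remain: censoring assumes that people who stop answering resemble those who continue, so reasons for loss of contact should be tabulated; and the change does not remove confounding from self-chosen treatment.

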**Procedures:**

Instrument	Duration	Assessment Time Points	Frequency
Baseline Intake Form Chart Review Form 04/1/19-present Baseline Demographics and past medical history	30 min	Initial study entry	Once
PHQ-9	5 min	Initial Study Entry	Weekly
GAD-7	5 min	Initial Study Entry	Weekly
Columbia Screener-recent	3 min	Initial study Entry	-----
Symptom Checklist	5 min	(included in baseline)	Daily assessments
Columbia Screener – since last visit	3 min	-----	Daily assessments
Physician Interview/Medication Prescription	40 min	Baseline	weekly

Drug Distribution		Once, at entry	monthly
Blood Draw for future assessment of cytokine levels	60 min	Baseline	Weekly, as possible
Chart Review Followup		At study exit, one month, 3 months, 6 months and one year after study exit	See notes to left 5 data points From 4/1/19- 4/1/23

**Physician Interview/Medication Prescription**

Interview includes :

- 1) Assessment for pregnancy, contraindicated medications and review of baseline intake
- 2) Explanation of risks and benefits of medication : see patient handout information sheet

**Blood Draw for Future Assessment of Cytokine Levels :**

- Not to exceed 2 blood draws per week or a total of 50 ml total over 8 weeks time period
- Outpatient blood draws will occur only if study participants have regular clinical care blood draws until adequate personal protection equipment (PPE) is available for use in research settings. Study outpatient blood draw will occur by appointment at UTMC Emergency Department in a negative pressure room. Outpatient blood draws will not be done until there is adequate PPE available for research study purposes.
  - Study participant and phlebotomist will be equipped in full PPE.
- Inpatient blood draws will occur during normal clinical care blood draws.
- Blood samples will be stored at -80 degrees F in the hospital laboratory freezers for future cytokine analysis

**Study Timeline :**

Fluoxetine to reduce the risk of morbidity and mortality with COVID-19 infection

ID	Task Name	Start	Finish	Duration	Q2 20			Q3 20			Q4 20			Q1 21			Q2 21					
					Apr	May	Jun	Jul	Aug	Sep	Oct	Nov	Dec	Jan	Feb	Mar	Apr	May	Jun			
1	Enroll Patients in Overall Study	4/1/2020	4/1/2021	262d																		
2	Enroll Patients in Fluoxetine Arm	4/1/2020	2/1/2021	219d																		
3	Enroll Patients in Cytokine Study	4/1/2020	10/1/2020	132d																		
4	Data Analysis	7/1/2020	7/1/2021	262d																		
5	DSMB Review 1	7/1/2020	7/1/2020	1d																		
6	DSMB Review 2	10/1/2020	10/1/2020	1d																		
7	DSMB Review 3	1/1/2021	1/1/2021	1d																		
8	DSMB Review 4	4/1/2021	4/1/2021	1d																		

#### **4) Planned data analysis**

Aim 1, 2, 3 : Descriptive statistics,

Compare rates of primary and secondary outcome measures in subjects receiving fluoxetine with those not receiving fluoxetine by Student t-test and Chi-square test as appropriate.

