#### b) **Method of treatment assignment**

Single arm patient centered clinical trial

At study entry, participants will consent study participation via daily monitoring and will choose whether to participate in the activity monitoring, cytokine assessment and drug treatment portions of the trial. Participants who do not choose to take fluoxetine will serve as the control subjects. Additionally, patients will have the choice weekly to decide to start, continue, or discontinue the fluoxetine. See figure below :

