#### c) **Inclusion/exclusion criteria**

Inclusion : Patients aged 18 and above, able to give informed consent

COVID-19 test positive or presumptive positive awaiting COVID testin or results by following criteria: fever, cough and shortness of breath

Overall Study Exclusion Criteria :

Unable to give informed consent  
Prisoner/ institutionalized patient  
Under age 18

Exclusion from Fluoxetine Arm:

Active bleeding requiring blood products  
Bipolar disorder not on mood stabilizing medication\*  
Known allergy or hypersensitivity to fluoxetine  
Currently taking the following medications : MAO I, pimozide, thioridine  
Currently taking hydroxychloroquine  
Pregnant or breastfeeding (pregnancy questionnaire attached)  
For hospitalized patients : QTc greater than 500 ms  
\*Hospitalized patient may be on hydroxychloroquine if QTc<500 and the primary attending approves

Exclusion from Blood Sample Provision:

Pregnant  
Self-report of under 110 pounds

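### The planned comparison does not say whether people barred from fluoxetine at entry, or enrolled after the fluoxetine arm closes, count as controls

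*Combined protocol and SAP*

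**What the plan says.** Section 4, Planned data analysis, states the comparison for Aims 1 to 3 in one sentence: "Compare rates of primary and secondary outcome measures in subjects receiving fluoxetine with those not receiving fluoxetine", by t-test or chi-square test. It names no analysis set, restriction or adjustment.

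Three other places bear on who is in the untreated group.

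- Section 3b (Method of treatment assignment): "Participants who do not choose to take fluoxetine will serve as the control subjects". It adds that "patients will have the choice weekly to decide to start, continue, or discontinue the fluoxetine", and points to a figure that the available text does not show.
- Section 3c (Inclusion/exclusion criteria): the exclusions for the study as a whole are a short list (consent, institutional status, age). A separate and longer list is headed "Exclusion from Fluoxetine Arm". A person on the second list but not the first can enrol, but cannot enter the fluoxetine arm.
- Study Timeline (section 3h): enrolment into the fluoxetine arm runs from 4/1/2020 to 2/1/2021, and enrolment into the overall study from 4/1/2020 to 4/1/2021.

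The Aim 1 sample size of 312 untreated and 624 treated assumes that "2/3 of patients who enter the trial will choose to take fluoxetine".

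**The concern.** Two kinds of participant are untreated for reasons other than their own choice. Some were ineligible for the drug at entry. Others arrived after the fluoxetine arm had closed and so have no treated patients enrolled at the same time. If both are pooled with true decliners, the control rate partly reflects people who could not have been treated, or a different point in the pandemic.

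This is separate from the self-selection that the design accepts. Self-selection cannot be removed by redefining the groups, but this component can. The fluoxetine-arm exclusions concern bleeding, psychiatric history, pregnancy and co-medication, so a different risk of hospitalization is plausible, in either direction. At stake are the false-positive rate and the size of the estimated effect on hospitalization, the only endpoint for which the plan calls its sample size achievable.

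**Working it through.** **Inputs from the documents.** Aim 1 risks of 10% and 5%, alpha 0.05, power 0.80, 2:1 allocation, 312 + 624 = 936 (section 3d); the two enrolment windows (Study Timeline). **Assumed:** the accrual pattern, the barred share and the risks in the barred and late groups. Two-thirds uptake is applied to eligible people who enter while the arm is open.

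**1. The plan's own figure.** With k = 2 and mean risk (0.10 + 2 × 0.05)/3 = 0.0667,
n = [1.960 √(1.5 × 0.0667 × 0.9333) + 0.8416 √(0.09 + 0.0475/2)]² / 0.05² = (0.5988 + 0.2839)² / 0.0025 = 311.6, so 312. The 312/624 reproduces as a two-sided test without continuity correction (power 0.800).

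**2. The calendar gap.** 4/1/2020 to 2/1/2021 is 306 days, and 2/1/2021 to 4/1/2021 is 59 days; 59/365 = 16.2%. The listed durations of 219 and 262 days match the weekday counts for the two windows, so the gap is not an isolated mistyped date.

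**3. Late share of the untreated group.** If a fraction L of entrants is late, the share is L / [L + (1 − L)/3].

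- L = 2%, 5%, 10%: 6%, 14%, 25%.
- L = 16.2% (even accrual): 936 × 59/365 = 151 late and 785 in time, of whom 523 are treated and 262 are not. The untreated group is 413, and 151/413 = 37% of it is late.
- All 936 enrolled before 2/1/2021: no late group.

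**4. False-positive rate with no drug effect, 37% late.** The untreated risk is p = 0.10 + 0.366 (r − 0.10), where r is the late risk. The chance of two-sided p < 0.05 is Φ[(d − 1.96 s₀)/s₁] + Φ[(−d − 1.96 s₀)/s₁], where d = p − 0.10, s₀ is the pooled and s₁ the unpooled standard error, and n = 413/523.

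| Late risk r | Untreated risk p | Apparent RR | False-positive rate |
|---|---|---|---|
| 11% | 10.4% | 0.96 | 5.4% |
| 12% | 10.7% | 0.93 | 6.6% |
| 15% | 11.8% | 0.85 | 15% |
| 20% | 13.7% | 0.73 | 41% |

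For r = 20%: d = 0.0366, s₀ = 0.0211, s₁ = 0.0214, and Φ(−0.22) = 0.41. With a 6% late share (n = 324/612) the same four risks give 5.0% to 6.1%.

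In the other direction at 37% late, r = 8% or 5% makes a true halving appear as RR 0.54 or 0.61, with power 72% or 50% against 83% without bias.

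**5. Barred at entry, no late group.** If 2% of entrants are barred, they are 0.02/(0.02 + 0.98/3) = 5.8% of the untreated group (n = 324/612). If 5% are barred, they are 13.6% (n = 343/593). At twice the 10% risk, the untreated risk is 10.6% or 11.4% and the false-positive rate is 6.1% or 10.4%.

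**6. Power for 10% against 5% after restriction.** Even accrual, late entrants removed: 262/523, 73%. All 936 in time with 0%, 2% or 5% barred: 80%, 79% or 78%. Under even accrual, 936 × 365/306 = 1,116 entrants would be needed to have 936 in the open window.

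**The case against.** **The plan may already settle it.** Section 3b describes controls by choice and refers to a figure that is not shown. This stands as a limit. A reader might infer that sections 3b and 4 contradict each other. They do not: people who had no choice can be read into or out of the group that did not choose. It is an unsettled definition, and the figure might resolve it.

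**Eligibility is probably known for decliners.** A reader might infer that it goes unrecorded, because pregnancy and contraindicated medications are checked in an interview paired with the prescription. The documents do not support that. The schedule lists the interview at baseline and weekly without limiting it to fluoxetine takers, medications and history are listed variables, and a pregnancy questionnaire is mentioned. Only a request to confirm remains.

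**The late group may be empty.** The timeline is a plan, and section 3d says of the 936: "This sample size is very achievable given the current coronavirus pandemic". This stands: the 37% requires even accrual, which nothing in the documents supports. The illustration also applies two-thirds uptake to open-window entrants, whereas section 3d words it as two-thirds of all entrants. That choice does not inflate the share: under even accrual the section 3d wording needs 624/785 = 80% uptake while the arm is open, and late entrants would then be 151/312 = 48% of the untreated group.

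**The larger bias is self-selection.** True, and restriction does not cure it. That is no reason to keep a second source of bias that a definition can remove.

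**Conclusion.** The concern holds as a gap in the definition of the comparison groups and should be fixed. As written, the analysis can count untreatable and non-concurrent people as controls, and nothing in the available text says otherwise. Confidence is medium because of the missing figure.

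The size is not established. The 41% false-positive rate needs even accrual and a doubled late risk together. It is the top of an assumed range and not a prediction. A reader might also infer that the bias favours fluoxetine. The documents give no risk for either group, and a lower risk would hide a real effect instead. With small late or barred shares and modest risk differences the consequence is slight.

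**What to change.** In section 4, define the primary comparison as participants who entered while the fluoxetine arm was open and who met the section 3c fluoxetine-arm criteria on entry data, applied in the same way to both groups. Report barred and late participants separately, or in a sensitivity analysis that includes all controls. Confirm that the entry data needed (medications, history, pregnancy) are captured for decliners too. Either align the two closing dates or state that late entrants do not count toward the 312; barred controls should not count toward it in either case.

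The cost is a few sentences and a smaller analysis set, with the power shown in step 6. The plan should therefore state that its 80% applies only if 936 people are in the concurrent, eligible set.

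The restricted comparison remains self-selected. How to classify people who start or stop in later weeks, and how to read the hydroxychloroquine footnote in section 3c, are separate questions that this change does not resolve.

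### The planned comparison of depression, anxiety and suicidal thinking between self-selected groups names no use of the entry measurements, which leaves an avoidable bias of unknown direction and loses precision.

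*Combined protocol and SAP*

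**What the plan says.** All references are to the combined protocol and SAP.

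- **Groups.** Section 3(b) forms them by patient choice: "Participants who do not choose to take fluoxetine will serve as the control subjects". The choice is reopened every week.
- **Outcomes.** Section 3(f) lists the secondary outcomes for Aims 1 and 2 as "Depression, Anxiety, Suicidal thinking, Days of Illness, Severity of Illness".
- **Measurements.** The Procedures table in section 3(h) schedules PHQ-9 and GAD-7 at entry and then weekly. Suicidal thinking is screened at entry with "Columbia Screener-recent" and daily afterwards with "Columbia Screener – since last visit". The Symptom Checklist is part of the baseline intake and is then daily.
- **Analysis.** Besides descriptive statistics, section 4 has one comparative sentence: "Compare rates of primary and secondary outcome measures in subjects receiving fluoxetine with those not receiving fluoxetine by Student t-test and Chi-square test", with the choice between the two tests left to what is appropriate. It names no covariate, change score, regression, stratification or follow-up time point.

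**The concern.** For depression and anxiety, the entry score is the outcome itself before treatment, and it will usually be a strong predictor of the later score. Nothing in the design balances it, because patients choose whether to take the drug. The documents themselves class fluoxetine with antidepressants (section 1), so mood at entry could plausibly influence that choice. A two-sample test on follow-up scores passes part of any starting difference into the apparent drug effect. Even if the groups happened to start level, the test would leave in the error term variation that the entry score could explain.

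At stake are the secondary comparisons of depression, anxiety and suicidal thinking. The powered hospitalization comparison has no entry value of its own and is not affected by this point.

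**Working it through.** **Inputs from the plan.** Section 3(d) says the calculations "are based on achieving the standards of a power of 0.80 and with an alpha of 0.05". Aim 1 assumes that "2/3 of patients who enter the trial will choose to take fluoxetine" and that "10% of COVID-19 + patients will progress to a clinical condition requiring hospitalization", halved to 5% on fluoxetine. The stated sizes are 312 and 624, total 936.

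**The plan's own figure.** Two proportions, pooled variance, two-sided, no continuity correction, 2:1 allocation:

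- Mean rate = (0.10 + 2 × 0.05)/3 = 0.0667.
- n = [1.96 × √(0.0667 × 0.9333 × 1.5) + 0.8416 × √(0.09 + 0.0475/2)]² / 0.05² = (0.5988 + 0.2839)² / 0.0025 = 311.6, so 312, with 624 on fluoxetine.

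The 936 is reproduced exactly. It implies a two-sided test, and this point does not alter it.

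**Assumptions not in the plan.** A continuous score with SD 1 in each group; correlation ρ between entry and on-study score of 0.5 (range 0.3 to 0.7); an entry gap g of 0.2 SD; a true effect of 0 or 0.20 SD; group membership fixed at 312 and 624; normal approximation, two-sided 0.05.

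**Standard error.** SE = √(1/312 + 1/624) = 0.0693 SD, so k = 1/SE = √(312 × 624/936) = 14.42.

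**Bias with no drug effect.** The unadjusted difference is centred on ρg. The rejection rate is that of a z-test with mean ρgk.

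**A true 0.20 SD benefit when takers start 0.2 SD worse.** The apparent benefit is 0.20 − ρg.

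| ρ | Bias ρg (SD) | ρgk | Significant with no drug effect | Apparent benefit (SD) | Its power |
|---|---|---|---|---|---|
| 0.3 | 0.06 | 0.87 | 13.9% | 0.14 | 0.524 |
| 0.5 | 0.10 | 1.44 | 30.3% | 0.10 | 0.303 |
| 0.7 | 0.14 | 2.02 | 52.4% | 0.06 | 0.139 |

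Without a gap, power for 0.20 SD is 0.822 (0.20 × 14.42 = 2.88). The spurious results fall almost wholly on one side: harm if takers start worse, benefit if they start better.

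**Precision with no entry gap.** Adjusting multiplies the variance by 1 − ρ², so power for 0.20 SD rests on 2.88/√(1 − ρ²).

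| ρ | Variance removed | 2.88/√(1 − ρ²) | Power (unadjusted 0.822) |
|---|---|---|---|
| 0.3 | 9% | 3.02 | 0.856 |
| 0.5 | 25% | 3.33 | 0.915 |
| 0.7 | 49% | 4.04 | 0.981 |

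**Does adjustment work when there is a gap?** With a 0.2 SD gap the adjusted SE is 0.958, 0.870 and 0.717 of the unadjusted SE for ρ = 0.3, 0.5 and 0.7, so little of the gain is lost. The bias was checked by simulation at a larger gap of 0.3 SD, with 4,000 trials per setting and no drug effect:

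- ρ = 0.5: t-test bias 0.152 SD, significant in 59.5%; adjusted bias 0.002 SD, significant in 4.4%.
- ρ = 0.7: t-test bias 0.210 SD, 85.6%; adjusted bias −0.001 SD, 4.9%.
- ρ = 0.5 with the gap reversed: t-test bias −0.149 SD, 57.0%, all toward benefit; adjusted bias 0.001 SD, 5.2%.

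**Would a t-test on change do instead?** When the entry score accounts for the follow-up gap, the bias of a change score is (ρ − 1)g. At g = 0.2 that is −0.14, −0.10 and −0.06 SD for ρ = 0.3, 0.5 and 0.7: the opposite sign, and no smaller until ρ exceeds 0.5. With no gap its SE is √(2(1 − ρ)) = 1.18, 1.00 and 0.77 times the unadjusted SE, against 0.95, 0.87 and 0.71 for the adjusted model.

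These figures are for continuous scores. None is offered for the binary suicidal-thinking outcome.

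**The case against.** **The plan is silent rather than wrong.** Section 4 does not say that raw follow-up scores will be compared, and a t-test on change would use the entry value. The descriptive statistics it promises might also include entry scores. It is fair to say the use of entry values is unspecified rather than ruled out. That does not rescue the plan: no change score is named, and a change score would carry its own bias here.

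**The direction is unknown.** A reader might infer that takers start more depressed and that fluoxetine will look harmful. The documents give no entry scores by group, do not place mood screening before the physician interview, and put the treatment choice at study entry with consent. Section 3(c) also bars some psychiatric patients from the fluoxetine arm but not from the study, which would put them among the controls. This objection stands, so the bias must be stated in both directions.

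**Suicidal thinking.** A reader might infer that ideation present at entry automatically counts against fluoxetine. It does not. The daily screen asks about the period since the last contact, so entry ideation counts only if it persists or recurs. The two versions cover different windows, which rules out a like-for-like change from entry.

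**Severity of illness.** A reader might add this to the list of outcomes with an entry value. Section 3(f) does not tie it to the Symptom Checklist, and nothing says that the checklist grades severity. The outcome ladder in section 3(g), from never hospitalized to death, is an equally plausible reading.

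**It is part of a wider problem.** These are secondary outcomes in what section 3(d) calls a pilot study, and one covariate-adjusted model for all outcomes could absorb the point. Weekly switching also means that the score behind a later start is that week's, not the entry score. Both remarks are right and limit what the fix achieves. The point still stands separately, because the remedy uses each outcome's own scheduled measurement and the precision loss arises without any confounding.

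**Conclusion.** The point holds for PHQ-9 and GAD-7 in full, and in kind though not in size for suicidal thinking. The analysis named in section 4 makes no stated use of the entry value. Under the assumptions above, a modest 0.2 SD gap is enough to raise the false-positive rate to roughly three to ten times its nominal 5%, in whichever direction the groups happen to differ.

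A reader might infer that a real benefit could be turned into apparent harm. The figures do not show that: at a 0.2 SD gap a true 0.20 SD benefit shrinks to 0.10 SD (0.14 to 0.06) but keeps its sign. Reversal needs ρg above 0.20, for example a gap above 0.4 SD at ρ = 0.5, and nothing in the documents points to a gap that large.

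The correlation, gap and effect are all assumed, and the groups are treated as fixed although patients may switch weekly. This is a change that should be made to secondary analyses; it does not affect the primary sample size.

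**What to change.** In section 4:

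1. Analyse PHQ-9 and GAD-7 with a linear model of the chosen on-study score on fluoxetine group plus the participant's entry score.
2. Do the same for severity of illness only if the plan states that it is scored from the Symptom Checklist.
3. For suicidal thinking, stratify by or adjust for the entry Columbia result, and report participants positive at entry separately.
4. Tabulate entry PHQ-9, GAD-7, Columbia and symptom results by group.

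This costs a few sentences and one table, using data already scheduled. A simple rule is needed for participants without an entry score. The adjustment deals only with the measured starting difference. It does not remove confounding by unmeasured factors or by the weekly decisions to start or stop, and the report should say so.
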